[figure not shown]

CLINICAL PROTOCOL

A PHASE 2, OPEN-LABEL, SINGLE-ARM STUDY TO EVALUATE EFFICACY AND SAFETY OF BOSUTINIB MONOTHERAPY IN JAPANESE ADULT PATIENTS WITH NEWLY DIAGNOSED CHRONIC PHASE CHRONIC MYELOGENOUS LEUKEMIA

Investigational Product Number:	PF-05208763, SKI-606
Investigational Product Name:	Bosutinib
United States (US) Investigational New Drug (IND) Number:	Not Applicable (N/A)
European Clinical Trials Database (EudraCT) Number:	Not Applicable (N/A)
Protocol Number:	B1871048
Phase:	2b

Document History

Document	Version Date	Summary of Changes and Rationale
Amendment 1	30 Mar 2018	
 • Made changes in study objectives/endpoints and interim analysis. • Added “MMR by 12 months” as a secondary endpoint and “interim look” prior to primary analysis to assess the possibility of early communication with regulatory authorities based on the interim data. This change affected Sections 2, 9.2.2.1 and 9.5. • Added “Time to MR^{4.0} and MR^{4.5}” as exploratory objectives and endpoints in Section 2 to be aligned with Section 9. • Split an exploratory objective and endpoint “MMR at 3, 6, 9, 12 (in patients with both Ph+ and Ph negative (-) CP CML) and 18 months” into two separated exploratory endpoints in Section 2 for clarification. • Removed a duplicated exploratory objective and endpoint related to evaluation of BCR-ABL mutations in Section 2. • Updated bosutinib information based on the results of Study AV001 and FDA approval for newly diagnosed CML in Section 1.2.4. • Incorporated changes of Protocol Administrative Change Letters. • Clarified the required timing of 24-hour urine protein and microscopic assessments in Table 4. • Eliminated the inconsistency in the items of hematology tests (SoA and Section 7.1.1) and the active collection periods of

Appendix 5. Selected Strong and Moderate CYP3A4 Isoenzyme Inhibitors and
Inducers.....84
Appendix 6. Guidelines for the Management of Diarrhea.....85

PROTOCOL SUMMARY

Background and Rationale

Bosutinib (Bosulif[®]) is an orally bioavailable, potent, multi-targeted, dual Src/Abl tyrosine kinase inhibitor (TKI) that has been approved in Japan and multinationally for the treatment of adult patients with Philadelphia chromosome (Ph)-positive(+) chronic phase (CP), accelerated phase (AP), and blast phase (BP) chronic myelogenous leukemia (CML) previously treated with other TKI inhibitor therapy.¹ In December 2017, bosutinib was additionally approved for adult patients with newly diagnosed Ph+ CP CML in the US. This study will investigate the efficacy and safety of bosutinib as a first-line treatment for Japanese adult patients with Ph+ CP CML.

In Japan, patients with newly diagnosed CML are now able to be effectively treated with TKIs, including imatinib, dasatinib, and nilotinib, with their disease controlled for long periods of time. Bosutinib may represent an additional choice for such patients for treatment of their CML in the first-line treatment setting, which could offer these patients a better tolerated and possibly more sustainable treatment option than other available therapies.

Prior clinical studies with bosutinib in CML have used a starting dose of bosutinib of 500 mg once daily (QD). In the previous studies, a substantial number of patients experienced toxicities. The incidence of treatment-emergent adverse events (TEAEs) overall as well as unique TEAEs were lower following dose reduction from 500 mg QD to 400 mg QD, while the efficacy of bosutinib in patients who received dose reductions to 400 mg QD remained favorable. Therefore, it was hypothesized that a starting dose of 400 mg QD in this Phase 2 study in the first-line Japanese CP CML patient treatment setting will result in better tolerability and similar efficacy as a starting dose of 500 mg QD.

Objectives and Endpoints

Primary Objective

- To evaluate major molecular response (MMR) at 12 months (48 weeks) in newly diagnosed Japanese Ph+ CP CML patients harboring b2a2 and/or b3a2 transcripts.

Secondary Objectives

All efficacy analyses for secondary/exploratory objectives will be performed using the same population as primary objective, unless otherwise indicated (detailed in Section 9). For detailed definitions of responses, see [Appendix 2](#).

- To evaluate MMR by 12 and 18 months.
- To estimate the proportion of patients demonstrating complete cytogenetic response (CCyR) by 12 months.

- To evaluate the duration of MMR and CCyR.
- To evaluate event-free survival (EFS).
- To evaluate overall survival (OS).
- To assess the population pharmacokinetics (PK).
- To assess correlations between trough concentrations of bosutinib and key efficacy and safety endpoints.
- To characterize the safety profile of bosutinib in Japanese patients.

Exploratory Objectives

- To evaluate MMR at 3, 6, 9 and 18 months.
- To evaluate MMR at 12 months in patients with both Ph+ and Ph negative (-) CP CML.
- To evaluate molecular response (MR)¹ and MR² at 3 months and 6 months, respectively.
- To evaluate MR^{4.0} and MR^{4.5} at 3, 6, 9 and 12 months.
- To evaluate time to MMR, MR^{4.0}, MR^{4.5} and CCyR.
- To evaluate the proportion of patients demonstrating a cumulative complete hematologic response (CHR) in patients with Ph+ and both Ph+ and Ph- CP CML.
- To estimate the time to transformation to AP and BP CML on treatment.
- To evaluate the type of BCR-ABL mutations present at treatment completion or discontinuation, or in case of suboptimal response.
- To enable exploratory research through collection of banked biospecimen, unless prohibited by local regulations or ethics committee (EC) decision.

Primary Endpoint

- MMR at 12 months (48 weeks). All Ph+ CP CML patients harboring b2a2 and/or b3a2 transcripts will be assessed and follow-up for MMR as primary endpoint. MMR is defined as $\leq 0.1\%$ BCR-ABL on the international scale (IS) by quantitative reverse transcriptase polymerase chain reaction (RT-qPCR).

Secondary Endpoints

- MMR by 12 and 18 months.

- CCyR by 12 months.
- Duration of MMR and CCyR.
- EFS
- OS
- Population PK parameters.
- Correlations between trough concentrations of bosutinib and key efficacy and safety endpoints.
- Safety: AEs (as graded by National Cancer Institute Common Terminology Criteria for Adverse Events [NCI CTCAE] v.4.03); laboratory abnormalities (as graded by NCI CTCAE v.4.03); vital signs (blood pressure, pulse rate); electrocardiograms (ECGs); echocardiogram (ECHO) or multiple gated acquisition (MUGA).

Exploratory Endpoints

- MMR at 3, 6, 9 and 18 months.
- MMR at 12 months in patients with both Ph+ and Ph- CP CML.
- MR¹ and MR² at 3 months and 6 months, respectively.
- MR^{4.0} and MR^{4.5} at 3, 6, 9 and 12 months.
- Time to MMR, MR^{4.0}, MR^{4.5} and CCyR.
- Cumulative CHR in patients with Ph+ and both Ph+ and Ph- CP CML.
- Time to transformation to AP and BP CML on treatment.
- Type of mutations present at treatment completion/discontinuation or suboptimal response.
- Potential results from exploratory analyses of banked biospecimen (these results may or may not be generated in the context of the present study).

Study Design

Study Overview

This is a Phase 2, open-label, single-arm study designed to evaluate efficacy and safety of bosutinib alone in Japanese adult patients with newly diagnosed CP CML. The primary

endpoint is MMR at 12 months in newly diagnosed Japanese Ph+ CP CML patients harboring b2a2 and/or b3a2 transcripts. Patients will receive bosutinib treatment at a starting dose of 400 mg QD. The dose of bosutinib is allowed to be escalated (up to a maximum of 600 mg QD) for unsatisfactory response or reduced for toxicity.

This study has approximately 52 weeks of planned patient accrual. Each patient will have 12 months (48 weeks) of Core Treatment Phase and the following ≥ 24 months (96 weeks) of Extension Phase. After treatment discontinuation, the patient enters Long-Term Follow-Up. The Extension Phase or Long-Term Follow-Up will continue until the end of the study.

The study will be open for enrollment until approximately 60 Ph+ CML patients harboring b2a2 and/or b3a2 transcripts have been registered. Bone marrow aspirate to assess the Ph status will be obtained at screening, patients with known Ph- prior to registration are not eligible for this study. However, as confirmation of the Ph status prior to registration is not mandatory, Ph- CML patients may also be included. Approximately 3 Ph- CML patients are expected to be registered as approximately 5% of the patients with BCR-ABL-positive CML are diagnosed as Ph- CML.^{2,3} All patients will be treated and/or followed up to approximately 3 years (144 weeks) after registration of the last patient, or until study termination, whichever comes first. Patients who permanently discontinue study treatment will be followed for survival, investigator-assessed transformation to AP/BP, duration of response and disease progression, and initiation/response to further anti-cancer therapies, including stem cell transplantation (where applicable).

Study Treatments

All patients will receive bosutinib at a starting dose of 400 mg QD. The dose of bosutinib may be escalated (up to a maximum of 600 mg QD) for unsatisfactory response or reduced (down to 300 mg QD, and further to a minimum of 200 mg QD only when approved by the sponsor) for toxicity.

Each patient will receive daily bosutinib for up to approximately 3 years after registration of the last patient (12 months [48 weeks] Core Treatment Phase and the following ≥ 24 months [96 weeks] Extension Phase) or until the end of the study, treatment failure, unacceptable toxicity, death, or withdrawal of consent, whichever occurs first.

Statistical Methods

The primary analysis population for the efficacy evaluation will be the modified as-treated population. The modified as-treated population will consist of all patients with Ph+ CP CML harboring b2a2 and/or b3a2 transcripts who received at least 1 dose of study medication.

The primary efficacy variable is MMR rate at 12 months (48 weeks) which is defined as the proportion of patients achieving MMR at 12 months (48 weeks). MMR is defined as BCR-ABL expression of $\leq 0.1\%$ of initial BCR-ABL transcript from standardized baseline measured by RT-qPCR.

Sample Size Determination

The primary analysis will use the hypothesis test for a binomial proportion the using normal approximation. The study is powered at greater than 82% to test the null hypothesis that the true MMR rate at 12 months (48 weeks) is 25% versus the alternative hypothesis that the true MMR rate is 40% with one-sided alpha of 5%. A sample size of 60 Ph+ CML patients harboring b2a2 and/or b3a2 transcripts is required for MMR at 12 months (48 weeks). Rejecting the null hypothesis and accepting the alternative hypothesis in the modified as-treated population (observing at least 21 responders out of the 60 total patients), will be considered to be a successful demonstration of efficacy for this study.

As cytogenetic confirmation for Ph chromosome is not required for enrollment and 5% of patients are expected to be Ph- CML, approximately 3 Ph- CML patients may be enrolled, which will not affect the primary analysis.^{2,3}

SCHEDULE OF ACTIVITIES

The SCHEDULE OF ACTIVITIES table provides an overview of the protocol visits and procedures. Refer to the [STUDY PROCEDURES](#) and [ASSESSMENTS](#) sections of the protocol for detailed information on each procedure and assessment required for compliance with the protocol.

The investigator may schedule visits (unplanned visits) in addition to those listed in the SCHEDULE OF ACTIVITIES table in order to conduct evaluations or assessments required to protect the well-being of the patient.

Visit Identifier ^a	Screening		Core Treatment Phase													Extension Phase	End of Treatment / Withdrawal
	0	0	1	1	1	1	1	2	2	3	3	4	5	6	9, 12		
Month	0	0	1	1	2	3	4	6	8	10	12	16	20	24	36, 48	Every 12 weeks up to 2 years, then every 24 weeks thereafter	7-28 days after the last dose of study drug
Week	0	0	1	1	2	3	4	6	8	10	12	16	20	24	36, 48		
Day	-28 to registration	-14 to registration	1	7	14	21	28	42	56	70	84	112	140	168	252, 336		
Visit Time Window			±4 days													±1 week	
Informed consent	X																
Registration			X														
Inclusion/Exclusion criteria review	X																
Demographic data collection		X															
Sokal score calculation ^b		X															
Medical ^c /Cancer history ^d review		X															
Physical examination ^e		X				X		X		X					X	X	X
Vital signs, weight, and height (screening only) ^f		X	X							X				X	X	X	X
ECOG performance status		X								X						X	X
Extramedullary assessment ^g		X				X		X		X					X	X	X
Digital ECG ^h		X	X			X		X		X						As clinically indicated	
Chest X-ray		X								As clinically indicated							X
Contraception check ^l	X		X			X		X		X	X	X	X	X	X	X	X
ECHO or MUGA ^l	X									As clinically indicated							X

Visit Identifier ^a	Screening		Core Treatment Phase													Extension Phase	End of Treatment / Withdrawal
	0	0	1	1	1	1	1	2	2	3	3	4	5	6	9, 12		
Month	0	0	1	1	2	3	4	6	8	10	12	16	20	24	36, 48	Every 12 weeks up to 2 years, then every 24 weeks thereafter	7-28 days after the last dose of study drug
Week	0	0	1	1	2	3	4	6	8	10	12	16	20	24	36, 48		
Day	-28 to registration	-14 to registration	1	7	14	21	28	42	56	70	84	112	140	168	252, 336		
Visit Time Window			±4 days													±1 week	
Laboratory Tests																	
Hematology including CBC with differential ^k		X		X	X	X	X	X	X	X	X	X	X	X	X	X ^y	X
Chemistry panel with electrolytes and CK ^l		X				X		X		X		X	X	X	X ^y	X	
Liver function tests ^m		X				X		X		X		X	X	X	X ^y	X	
Estimated glomerular filtration rate		X				X		X		X		X	X	X	X ^y	X	
Coagulation panel ⁿ		X								X					X ^y	X	
HBV and HCV test		X															
Dipstick urinalysis (microscopic if abnormalities detected)		X				X				X					X ^y	X	
Serum or urine pregnancy test (for women of childbearing potential)	X		X			X		X		X	X	X	X	X	X ^y	X	
Study Treatment																	
Study drug administration ^o			Continuous daily from Day 1														
Disease Assessments																	
Bone marrow aspirate ^p for cytogenetics ^q and differential	X ^p										X ^q		X	X ^p	X	X ^p	
Peripheral blood for local RT-qPCR for BCR-ABL		X ^r															
Peripheral blood for central RT-qPCR for BCR-ABL ^s and mutation analysis ^t		X								X		X	X	X	X	X	
Other Clinical Assessments																	
Adverse events ^u			X	→	→	→	→	→	→	→	→	→	→	→	→	→	X
Concomitant medications ^v	X	→	→	→	→	→	→	→	→	→	→	→	→	→	→	→	X
Other Samplings																	
PK blood sample collection ^w			X			X		X		X							
Banked blood biospecimens ^x		X															

Visit Identifier ^a	Screening		Core Treatment Phase													Extension Phase	End of Treatment / Withdrawal	
Month	0	0	1	1	1	1	1	2	2	3	3	4	5	6	9, 12	Every 12 weeks up to 2 years, then every 24 weeks thereafter	7-28 days after the last dose of study drug	
Week	0	0	1	1	2	3	4	6	8	10	12	16	20	24	36, 48			
Day	-28 to registration	-14 to registration	1	7	14	21	28	42	56	70	84	112	140	168	252, 336			
Visit Time Window				±4 days													±1 week	
Other																		
Long-term follow-up ²																X		

Abbreviations: → = ongoing/continuous event; BCR-ABL = Fusion transcript or protein resulting from the 9;22 chromosomal translocation responsible for formation of the Philadelphia Chromosome; CBC = complete blood count; CK = creatine kinase; ECG = electrocardiogram; ECHO = echocardiogram; ECOG = Eastern Cooperative Oncology Group; HBV = hepatitis B virus; HCV = hepatitis C virus; MUGA = multiple gated acquisition; PK = pharmacokinetics; RT-qPCR = Quantitative reverse transcriptase polymerase chain reaction.

- a. Day relative to start of study treatment (Day 1).
- b. Every effort should be made in order to have Sokal score calculated prior to any anti-CML treatments (ie. at initial diagnosis of patient). Sokal formula is $Exp(0.0116 \times (age - 43.4) + 0.0345 \times (spln - 7.51) + 0.188 \times [(plt/700)^2 - 0.563] + 0.0887 \times (blasts - 2.1))$; Note: Spln=centimeters below costal margin, plt=platelet count, $10^9/L$, blasts=% blasts in peripheral blood. If the patient has already received anti-CML treatment prior to screening every effort should be made to obtain test results/data before the start of treatment in order to calculate the Sokal score. If patient did not have prior anti-CML treatment, the Sokal score will be calculated using data obtained at screening.
- c. Medical history review includes clinically significant past and current diagnoses (including complete cardiac history) and surgical procedures.
- d. Cancer history review includes full history of the course of the patient's cancer including date of diagnosis and any prior treatments, history of blood and platelet transfusions or history of lumbar punctures within 28 days prior to registration.
- e. Complete physical examination ensuring examination of liver and spleen will be performed.
- f. Vital signs include temperature (axillary), supine blood pressure, and heart rate. Height will be measured at screening only.
- g. Extramedullary assessment will include physical examination and based on this assessment and any specific evidence, appropriate imaging testing can be requested by the investigator. The assessment should be done at any time if extramedullary disease is suspected.
- h. Digital ECGs to be done in triplicate at each time point and should be performed at the same as PK sampling (if applicable). End of Treatment/Withdrawal visit ECG should be done at least 5 days after the last dose of bosutinib and prior to initiating other anticancer treatment (if possible). ECG should also be performed if clinically significant decrease in ejection fraction is detected by ECHO/MUGA while on treatment, and otherwise as clinically indicated.
- i. Male patients who are able to father children and female patients who are of childbearing potential will need to follow the contraception guidelines in Section 4.3.
- j. ECHO or MUGA to be performed at screening (within 2 weeks prior to registration) and at End of Treatment/Withdrawal or at Week 96, whichever is earlier. If a patient has undergone ECHO or MUGA as standard of care prior to entering the study, the procedures will not have to be repeated if results are available and the procedures were performed within 28 days prior to registration. To enable meaningful clinical comparison, every effort must be made to ensure that the imaging method used to assess cardiac function remains consistent for each individual patient through the course of the trial.

- k. Hematology including automated complete blood count (CBC) (eg, hemoglobin, RBC, WBC, platelets and hematocrit) with differential counts (eg, neutrophils, lymphocytes, monocytes, eosinophils, basophils, metamyelocytes, myelocytes, promyelocytes, myeloblasts, unspecified blast cells and band cells) to be performed locally. Hematology assessments are to be performed at Screening, Weeks 1, 2, 3, 4, 6, 8, 10, 12, 16, 20, 24 and then every 12 weeks for the next 72 weeks (ie, until the end of Year 2), then every 24 weeks, and End of Treatment/Withdrawal visit. CHR must be confirmed by 2 assessments at least 4 weeks apart. Hematology to be repeated at least 4 weeks after achieving first CHR.
- l. Chemistry panel to be performed locally including: sodium, potassium, chloride, carbon dioxide or bicarbonate (if available), blood urea nitrogen (BUN) or urea, creatinine, glucose, total protein, albumin, calcium, alkaline phosphatase, amylase, lipase, phosphorous or phosphate, and magnesium. Creatine kinase (CK) also to be performed locally. Abnormally high CK values should be confirmed and fractionated (where possible). Uric acid to be obtained until patient achieves a CHR. Supplementation is advised for potassium levels or magnesium levels below the lower limit of normal (LLN), with consideration of the patient's underlying renal function.
- m. Liver Function tests to be performed locally including: total bilirubin, aspartate aminotransferase (AST) and alanine aminotransferase (ALT).
- n. Coagulation panel to be performed locally including: prothrombin time (PT) expressed as either PT or international normalized ratio (INR) and partial/activated partial thromboplastin time (PTT or aPTT).
- o. The first dose of study drug should occur no later than 3 business days after registration of the patient, with the day of first study drug administration = Day 1.
- p. Bone marrow obtained as part of standard of care prior to signing informed consent document can be used at screening as long as it was collected within 28 days prior to registration. **Once CCyR or MMR has been achieved, bone marrow aspirates will be performed only if clinically indicated (eg, suboptimal response, suspect disease progression or failed/inadequate Week 48 assessment).** Patients completing treatment for cytogenetically confirmed treatment failure do not need to repeat bone marrow at treatment completion. Patients ending treatment for reasons other than cytogenetically confirmed treatment failure must undergo treatment completion bone marrow aspirate if previous bone marrow aspirate performed >12 weeks prior. If loss of major molecular response occurs in combination with a $5 \times$ PCR increase for BCR-ABL, a bone marrow aspirate for chromosome banding analysis (CBA) should be obtained.
- q. Cytogenetics analysis must be performed so that dose-escalation rules can be appropriately applied (eg, patient should not have 12-week bone marrow aspirate before Day 84 so that at least 12 weeks from first dose is assessed). Cytogenetic assessment of bone marrow aspirate will be performed locally. If cytogenetics is used, it must be performed by CBA of marrow cell metaphases, counting at least 20 metaphases, at 12, 24, 36, and 48 weeks, until CCyR or MMR is achieved, then every 48 weeks.
- r. Local PCR result for BCR-ABL confirmation is acceptable prior to informed consent where this has already been conducted as part of initial diagnosis of a patient, provided this molecular diagnosis of CP CML has been made ≤ 6 months prior to registration. However, central PCR sample must always be conducted after informed consent, as this is a study-specific procedure.
- s. RT-qPCR testing for BCR-ABL will be performed at Screening, at 12, 24, 36, and 48 weeks during the Core Treatment Phase and then every 12 weeks until the end of Year 2, then every 24 weeks. If a ≥ 5 -fold increase in BCR-ABL transcripts from the lowest value achieved on study along with loss of MMR is identified and confirmed by duplicate analysis of the same sample, an unscheduled visit sample will be collected within 4-6 weeks to confirm the results. Fifteen (15) mL peripheral blood will be collected at each designated time-point. Additional 5 mL blood will be collected at Week 48; these will serve as back-up samples for the primary endpoint. For patients who achieve undetectable BCR-ABL by RT-qPCR, 20 mL of blood may be collected for PCR analysis. In addition, after the first documented negative BCR-ABL result, 20 mL of blood will be collected for all subsequent sampling time-points until BCR-ABL is no longer negative. 20 mL of blood may be collected as an unscheduled PCR sample from these patients.
- t. Mutation analysis will be performed in case of either lack of response, suboptimal response or loss of response defined as: failure to achieve MMR at 12 months; loss of MMR AND rise in BCR-ABL transcript level by ≥ 5 -fold from the lowest value achieved during the study; at the End of Treatment/Withdrawal visit. No mutation analysis will occur at screening. For patients with a positive mutation identified during therapy, follow-up

mutation analyses will be performed in subsequent samples. For a patient with a negative mutation result immediately following relapse, continued mutation analyses may be performed at a frequency of every 6 months (every 24 weeks) as needed.

- u. AEs should be documented and recorded at each visit using the NCI CTCAE version 4.03. The time period for actively eliciting and collecting AEs and SAEs (“active collection period”) for each patient begins from the time the patient provides informed consent through and including a minimum of 28 calendar days after the last investigational product administration. If a patient begins a new anticancer therapy, the period for recording non-serious AEs on the CRF ends at the time the new treatment is started. However, any SAEs occurring during the active collection period must still be reported to Pfizer Safety and recorded on the CRF, irrespective of any intervening treatment.
- v. All concomitant medications and non-drug supportive interventions will be recorded in the CRF from 28 days prior to registration and up to 28 days after the last dose of study treatment.
- w. The pre-dose PK samples should be collected before (within 3 hrs of) study drug administration on Days 1, 28, 56, and 84. 3 mL of whole blood for plasma drawn into a tube containing potassium ethylenediaminetetraacetic acid (EDTA). See Section 7.3. On PK sampling days, the bosutinib dose should be taken in the hospital under the supervision of the study site personnel. The bosutinib dose should be administered after the PK sample has been collected.
- x. Blood sample will be collected for bio-banking if specifically allowed by local Institutional Review Board (IRB) or EC; 1 tube of whole blood (prep D1) will be collected at Screening. If not collected on the designated collection day, collect at the next available time point when bio-specimens are being collected in conjunction with a patient visit.
- y. For patients remaining on treatment in the Extension Phase, the investigator should continue to perform biochemistry and hematology testing, per standard of care for CML patients and as clinically indicated in line with local guidelines including cytogenetics when indicated by bone marrow analysis. Patients will have mandatory AE and SAE collection follow-up. These are expected to take place at least every 12 weeks.
- z. Long-Term Follow-Up information will be collected via telephone contact up to approximately 3 years after registration of the last patient, or until study termination, whichever comes first, where possible for patients who discontinue the study early. Follow-up calls should be conducted every 12 weeks in the first two years, and then every 24 weeks. The timing of follow-up calls is calculated with Day 1 designated as the starting point.

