6.4. End of Treatment/Withdrawal Visit

For End of Treatment/Withdrawal visit procedures, see [SCHEDULE OF ACTIVITIES](#) table and [ASSESSMENTS](#) section.

Patients who discontinue from study treatment for any reason should complete an End of Treatment/Withdrawal visit between 7 and 28 days after the last dose of study drug, and the patient enters Long-Term Follow-Up.

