8.1.4. Time Period for Collecting AE/SAE Information

The time period for actively eliciting and collecting AEs and SAEs (“active collection period”) for each patient begins from the time the patient provides informed consent, which is obtained before the patient’s participation in the study (ie, before undergoing any study-related procedure and/or receiving investigational product), through and including a minimum of 28 calendar days after the last administration of the investigational product.

For patients who are screen failures, the active collection period ends when screen failure status is determined.

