#### 3.5.1. Adverse Events

An adverse event (AE) is any untoward medical occurrence in a study patient administered a product or medical device; the event need not necessarily have a causal relationship with the treatment or usage.

A treatment-emergent adverse event (TEAE) is defined as an AE that first occurred or worsened in severity from the first dose of the study drug until 28 days after the last dose. TEAEs will be assessed mainly in this study.

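### Adverse events are to be actively elicited to at least day 28 after the last dose, but the last scheduled AE contact can be as early as day 7

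*Protocol*

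**What the plan says.** **Collection period.** Protocol Section 8.1.4 runs active eliciting and collecting of AEs and SAEs "through and including a minimum of 28 calendar days after the last administration of the investigational product". Footnote u of the Schedule of Activities sets the same period, "through and including a minimum of 28 calendar days after the last investigational product administration", and adds the mechanism: "AEs should be documented and recorded at each visit using the NCI CTCAE version 4.03". Footnote v and Section 5.7 record concomitant medication up to day 28 after the last dose.

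**Analysis window.** SAP 3.5.1 defines a TEAE as an AE that starts or worsens "from the first dose of the study drug until 28 days after the last dose". Protocol 9.4.1 uses the same limit.

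**Last scheduled assessment.** In the Schedule of Activities, the AE and concomitant-medication rows end with a mark in the End of Treatment/Withdrawal column. That column is timed "7-28 days after the last dose of study drug". Section 6.4 says that a patient who stops treatment should complete an "End of Treatment/Withdrawal visit between 7 and 28 days after the last dose of study drug, and the patient enters Long-Term Follow-Up".

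**After that visit.** Footnote z provides telephone contact: "Follow-up calls should be conducted every 12 weeks in the first two years, and then every 24 weeks". These calls are counted from Day 1 of treatment, not from the last dose. Section 3 lists what is followed after discontinuation: survival, transformation to AP/BP, duration of response and progression, and further anti-cancer therapy. AEs are not on the list. The mandatory AE collection at least every 12 weeks in footnote y is written for patients who remain on treatment in the Extension Phase.

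**The concern.** The period over which AEs are to be elicited and the visit that ends the scheduled assessments do not match. The visit is allowed "between 7 and 28 days after the last dose of study drug", so only a visit on day 28 covers the whole period. A site that follows the schedule exactly and sees the patient on day 7 has done everything the table asks, yet three weeks of the TEAE window are still to come with nothing scheduled in them.

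New AEs and SAEs that begin in those weeks are then less likely to be recorded, and how much is lost depends on when each site books the visit. Safety is a secondary endpoint. There is no control arm, and the SAP shapes several AE outputs for comparison with study AV001. Capture that varies with visit booking makes that comparison harder to read. Patients who stop because of toxicity are among those affected.

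The protocol also gives sites a reason to book early. Footnote h asks for the End of Treatment ECG at least 5 days after the last dose and, if possible, before other anticancer treatment starts.

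**Working it through.** The documents state no figure for this gap, so there is none to reproduce. The check is a day count plus a search for any other scheduled contact.

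**Inputs**
- Visit window: day 7 to day 28 after the last dose (Schedule of Activities; Section 6.4).
- End of the TEAE window: day 28 (protocol 9.4.1; SAP 3.5.1). Active collection runs to at least day 28 (footnote u; Section 8.1.4).
- Long-Term Follow-Up calls: every 12 weeks (84 days) for two years, then every 24 weeks (168 days), counted from Day 1 (footnote z).
- Treated patients: 60 Ph+ plus about 3 Ph- = about 63 (Section 9.1).

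**Step 1: days without a scheduled AE contact.** With the visit on day v, the gap is 28 − v.
- v = 7: 28 − 7 = 21 days (days 8 to 28), 21/28 = 75%.
- v = 14: 14 days, 50%.
- v = 21: 7 days, 25%.
- v = 28: 0 days.

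The maximum is therefore 21 of 28 days.

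**Step 2: can a follow-up call close the gap?** The calls are tied to Day 1, so one falls on days 8 to 28 after the last dose only by coincidence. Assume that the last dose is equally likely to fall anywhere in the call interval:
- 12-weekly calls: 21/84 = 25% of patients.
- 24-weekly calls: 21/168 = 12.5% of patients.

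Even then, AEs are not listed as content of the call.

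**Step 3: other provisions that might close it.**
- Footnote y covers patients still on treatment, so it does not apply.
- Sections 8.1.4.1 and 8.1.4.2 deal with follow-up of events once they are known. They do not schedule a contact to find new ones.
- Section 8.1.2 requires non-leading questioning of each patient, but sets no time for it after the last dose.
- The contact efforts in Section 6.3 are triggered by a missed scheduled visit, and none is scheduled here.

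**Step 4: how many patients.** Only patients who have ended treatment have this visit. The documents do not give the number expected at the primary analysis. As an illustration, Section 1.2.3 reports 37% discontinuation on bosutinib in the earlier Phase 3 study (BELA). If that applied, 0.37 × 63 = 23.3, about 23 patients. This is an assumption: that study started at 500 mg and had at least 24 months of follow-up, whereas this study starts at 400 mg and its primary analysis follows 48 weeks of treatment. More patients will have ended treatment by the final analysis.

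For scale, one missed patient in an incidence table is 1/63 = 1.6 percentage points. That is a unit of size, not an estimate of how many would be missed.

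**The case against.** The strongest reply is that the duty already exists. Section 8.1.4 calls for active elicitation through at least day 28, and Section 8.1.2 requires each patient to be questioned. A site that sees the patient on day 7 and asks nothing further departs from the protocol. **This stands.** A reader might infer that late events would be found only if the patient volunteers them. The text does not support that. What is missing is a scheduled contact that carries out the requirement.

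Four other inferences go further than the documents allow:
- **Deaths.** A reader might add deaths on days 8 to 28 to the loss. Patients who discontinue are followed for survival, and OS needs death or last-alive dates (SAP 3.2.5). Such a death would surface later and be classified by its date.
- **Unresolved events.** Events present at the visit are already recorded. Section 8.1.4.1 continues follow-up of SAEs until they resolve or stabilise, and Section 8.1.4.2 provides that such follow-up may be required for events on the CRF.
- **A full 28-day gap for everyone who stops.** Recording of non-serious AEs ends when a new anticancer therapy starts (footnote u; Section 8.1.4.2). For patients who switch early, the gap in non-serious AEs is shorter; SAE collection continues.
- **Totals over all 63 patients.** Multiplying 63 by the gap assumes that everyone has ended treatment. SAP 6.6.1 tabulates event counts and incidence, not rates per patient-day, so a patient-day total does not convert into bias in a planned result.

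There is also no arm-to-arm bias in a single-arm study, and the primary endpoint is untouched. These limits reduce the consequence but leave the mismatch in place.

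**Conclusion.** The point holds as a gap in scheduled AE contact, not in the obligation to collect. Up to 21 of the 28 days after the last dose (days 8 to 28) have no scheduled AE or concomitant-medication contact, and neither footnote y nor the Long-Term Follow-Up calls reliably fills them. The 21 days is an upper bound, reached with a visit on day 7, and the gap is nil with a visit on day 28.

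What is exposed is AEs and SAEs with new onset after an early End of Treatment visit. The number of patients concerned at the primary analysis is unknown. The figure of about 23 of 63 rests on the borrowed 37%, and the 25% and 12.5% rest on uniform timing. The documents give no basis for estimating how many events would be missed. The effect is probably modest, but the correction is cheap and makes collection match the window that both documents use.

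**What to change.** In the Schedule of Activities, footnotes u and v, and Section 6.4, state that if the End of Treatment visit takes place before day 28 after the last dose, one separate AE/SAE and concomitant-medication contact is held on or shortly after day 28. A telephone call is enough.

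Leave the Long-Term Follow-Up calls in footnote z as they are. Moving the first of them to day 28 would conflict with their Day 1 anchor.

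The cost is one extra call for each affected patient, through a channel that the protocol already uses, and a reported TEAE rate that may be slightly higher because capture is more complete. No analysis or treatment rule changes.
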